## SYNOPSIS

Name of Sponsor/Company: Origin Biosciences, Inc. (Origin); previously; Alexion Pharmaceuticals, Inc. (Alexion)	
Name of Investigational Product: ORGN001 (formerly ALXN1101)	
Name of Active Ingredient: Cyclic pyranopterin monophosphate monohydrobromide dihydrate	
Title of Study: A Phase 2, Multicenter, Multinational, Open-Label, Dose-Escalation Study to Evaluate the Safety and Efficacy of ORGN001 (formerly ALXN1101) in Pediatric Patients with Molybdenum Cofactor Deficiency (MoCD) Type A Currently Treated with Recombinant Escherichia coli -derived Cyclic Pyranopterin Monophosphate (rcPMP)	
Study centers: This will be a multicenter, multinational study with approximately 5 investigational study centers.	
Principal Investigator: TBD	
Investigators: TBD	
Studied period: 6-Month Initial Treatment Period, followed by an Extension Period Estimated date first patient enrolled: February 2014 Estimated date last patient completed: The Extension Period is expected to last until ORGN001 is commercially available or development is stopped.	Phase of development: 2/3

Study Rationale
 
Molybdenum cofactor deficiency (MoCD) is a rare, life-threatening, autosomal recessive, inborn error of metabolism characterized by disruption of the metabolic pathway for production of molybdenum cofactor (MoCo), which is essential for the function of sulfite oxidase (SO), [REDACTED] dehydrogenase, and aldehyde oxidase. While all 3 enzymes are dependent on MoCo, the loss of SO activity is responsible for the severe and rapidly progressive neurologic damage seen in MoCD.
 
The incidence of MoCD is estimated to be between 1/100,000 and 1/200,000 newborn babies worldwide (Schwahn 2015). Affected individuals usually present as neonates with severe symptoms such as intractable seizures, burst-suppression or multifocal electroencephalogram (EEG), exaggerated startle reactions, axial hypotonia, limb hypertonia, and feeding difficulties. Neuronal injury is severe and is rapidly progressive as a result of accumulation of toxic levels of sulfite in the brain and subsequent formation of S-sulfocysteine (SSC). Death commonly occurs in the neonatal period, and patients who survive that period develop a severe static encephalopathy and developmental delay due to central nervous system (CNS) injury including subcortical cystic cavitation, hydrocephalus, diffuse cortical atrophy, and basal ganglia injury. At present, there is no cure.
 
Although there are 3 types of MoCD, two-thirds of MoCD patients have Type A, which is due to a mutation in the MOCS1 gene localized on 6p21.3. In MoCD Type A, the first of the 4 synthetic steps in the formation of MoCo is interrupted, and guanosine triphosphate (GTP) cannot be converted into cyclic pyranopterin monophosphate (cPMP). Diagnosis of MoCD Type A is based on clinical presentation and biochemical phenotype (such as elevated urinary sulfite and/or SSC, and low or absent uric acid in the urine or plasma), and diagnosis is then confirmed by genetic testing.
 
ORGN001 (cyclic pyranopterin monophosphate monohydrobromide dihydrate), provides a therapeutic approach for the treatment of MoCD Type A by restoring the MoCo biosynthesis. Results of preclinical pharmacology studies with ORGN001 suggest that the metabolic derangement in MoCD Type A could be corrected by administration of synthetic cPMP, resulting in restoration of enzymatic activity and thus, correction of the metabolic pathways that would otherwise lead to the accumulation of toxic metabolites causing CNS injury.
	

These results are supported by data obtained in pediatric patients with MoCD Type A treated with a recombinant *Escherichia coli*-derived cPMP product (rcPMP) from Colbourne Pharmaceuticals GmbH (Colbourne) [REDACTED]. Published individual case reports suggest that intravenous (IV) administration of rcPMP restores MoCo-dependent enzyme activities as evidenced by the reduction in levels of biomarkers of the disease (eg, SSC in urine) and improvement in neurologic outcome. This study is designed to evaluate the safety and efficacy of escalating doses of ORGN001 in pediatric patients with MoCD Type A currently treated with rcPMP.

### Objectives

#### Primary:

To evaluate the safety of ORGN001 over the first 6 months of treatment

#### Secondary:

- To characterize the pharmacokinetics (PK) of increasing doses of ORGN001
- To evaluate the effect of ORGN001 on urine and blood SSC levels
- To evaluate the effect of ORGN001 on neurologic, motor, and cognitive functions over time
- To evaluate the effect of ORGN001 on CNS structure
- To evaluate the long-term safety of ORGN001

### Endpoints

The following endpoints will be measured over the first 6 months of treatment and over the entire treatment period:

#### Safety:

- Incidence and severity of adverse events (AEs) and serious adverse events (SAEs)
- Incidence of clinical laboratory abnormalities
- Change from baseline in clinical laboratory assessments
- Change from baseline in clinical findings from physical examination
- Change from baseline in vital sign measurements
- Change from baseline in EEG results

#### Efficacy:

- Change from baseline in urine and blood SSC levels
- Change from baseline in clinical findings from neurologic examination
- Change from baseline in age-appropriate motor and cognitive assessments (Bayley Scales of Infant and Toddler Development-Third Edition [Bayley-III], The Gross Motor Function Classification System [GMFCS], Wechsler Preschool and Primary Scale of Intelligence [WPPSI])
- Change from baseline in seizure frequency
- Change from baseline in neuroimaging
- Changes in growth parameters (body weight, body length, head circumference)
- Change from baseline in feeding patterns

#### Pharmacokinetic:

- Pharmacokinetic parameters of ORGN001 including, but not limited to, maximum observed plasma concentration ( $C_{max}$ ), time to maximum observed plasma concentration ( $t_{max}$ ), area under the plasma concentration-time curve (AUC) and if possible, terminal half-life ( $t_{1/2}$ ) and dose linearity

**Methodology:**

This Phase 2, multicenter, multinational, open-label, dose-escalation study is designed to evaluate the safety and efficacy of ORGN001 administered to infants and children with MoCD Type A currently treated with rcPMP.

This study will include a Screening Period (Days -21 to Day -1), a 6-Month Initial Treatment Period, which includes escalating doses of ORGN001 after the first 2 months of ORGN001 treatment (Day 1 [first dose of study drug] to Day 180), and an Extension Period (post Day 180). A patient may be discontinued once ORGN001 is registered and available as a treatment for MoCD Type A in the region where the patient resides or is receiving treatment (in accordance with country--specific requirements).

Screening evaluations will be performed at any time during the Screening Period before the first dose of ORGN001. Enrolled patients will attend at least 2 study visits in order for baseline data to be obtained. During the Screening Period, patients will continue to receive daily IV infusions of their current rcPMP treatment.

During the 6-Month Initial Treatment Period, starting on Day 1, patients will begin IV infusions of ORGN001 at the same dose as their current dose of rcPMP, approximately 24 hours after their last treatment with rcPMP. No further treatments with rcPMP will be allowed during the study. Patients

patients will continue to receive daily infusions of ORGN001 at home and will attend multiple study visits for safety, efficacy, pharmacodynamic (PD), and PK assessments through Day 180. After the first 2 months of treatment with ORGN001, if the patient's clinical, PK, and safety assessments permit (including the absence of signs and symptoms of drug-related toxicity), dosing with ORGN001 will increase every month based on the patient's clinical response, safety laboratory assessments, and when appropriate, ORGN001 exposure data. Dose escalation will continue until either 1) Day 180, 2) the patient reaches a dose that is not tolerated, 3) the patient's exposure exceeds that of the no observed adverse effect level (NOAEL) AUC, or 4) the patient's exposure following dose escalation is predicted to exceed that of the NOAEL, whichever comes first. After the 6-Month Initial Treatment Period, patients will enter the Extension Period and continue to receive uninterrupted daily dosing of ORGN001 at their final tolerated dose based on the dose escalation. During the Extension Period, patients who were de-escalated from the final tolerated dose for reasons other than safety or PK considerations may be re-escalated up to their maximally tolerated dose. After dose escalation is complete, the patient can be returned to a prior dose based on the patient's clinical status at the discretion of the treating physician after consultation with the Safety Review Committee (SRC). Patients who prematurely discontinue from the study will attend a Safety Follow-up Visit and return to the care of their treating physician.

In order to monitor patient safety of ORGN001, patient data will be reviewed daily by the Principal Investigator (PI) or designee during the first 2 weeks following initiation of ORGN001. In addition, an SRC,

will review all available clinical data after each patient has completed the first 2 weeks of treatment with ORGN001, prior to each patient's scheduled dose escalations and at any other time during the study as requested by the PI or Sponsor. Based on the review of the available data, which may include laboratory data, clinical assessments, neuroimaging (if needed), and exposure data, the SRC, in consultation with an independent, external Data Monitoring Committee (DMC), may recommend stopping, increasing, decreasing, or maintaining the dose of ORGN001.

In addition to the scheduled dose escalations, a PI may identify the need for a dose adjustment in a patient based on the available data, including study drug-related AEs and/or changes in clinical parameters, and will convene the SRC to determine if an unscheduled dose adjustment is warranted. Blood and urine samples will be collected for PD and PK assessments on the first Day the adjusted dose is administered. PD and safety laboratory assessments will be repeated at the Follow-up Visit.

In addition, the SRC chair will request that the DMC convene if any of the criteria to hold dose escalation occur, or at any time during the study, as needed.

**Number of patients (planned):**

At least 4 patients with MoCD Type A will be enrolled in the study. The actual sample size will depend on the number of eligible patients currently treated with rcPMP.

**Diagnosis and main criteria for inclusion****Inclusion criteria:**

Patients must meet all of the following criteria to be enrolled in the study:

1. Male or female patients with a genetically confirmed diagnosis of MoCD Type A (MOCS1 mutation)
2. Currently treated with rcPMP infusions
3. Parent or legal guardian must have signed the informed consent form (ICF) prior to any study procedures

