#### 1.5 Rationale for Proposed Dosing

Patients will receive IV infusions of ORGN001 at the same dose as their current dose of rcPMP administered at a rate of 1.5 mL/minute.

ORGN001 drug product has been developed for IV use. Administration via the parenteral route is one of the best options because it provides rapid and consistent onset of action necessary for treatment of MoCD patients. Furthermore, the dose is easy to adapt to body weight, allowing greater dosing accuracy and more flexibility in case an adjustment of the dose is required.

The proposed starting doses are based on the safety and clinical effects reported with rcPMP. The dosing regimen in patients currently treated with rcPMP has been guided by clinical improvement and urine levels of SSC and thiosulfate (Veldman et al, 2010; Veldman et al, 2011; Schwahn et al, 2011; Hitzert et al, 2012). ORGN001 is expected to have similar pharmacodynamic (PD) effects since comparable activities on SO reconstitution and MPT restoration were reported with ORGN001 and rcPMP *in vitro* (Clinch et al, 2013). [REDACTED]

Based on the above observations, a dose-escalation scheme will be implemented in this study. Patients will start ORGN001 IV infusions at the same dose level as their current dose of rcPMP. The starting dose will be maintained for 2 months. After the first 2 months of treatment with ORGN001, if the patient's clinical, PK, and safety assessments permit (including the absence of signs and symptoms of drug-related toxicity), dosing with ORGN001 will increase every month [REDACTED] until either 1) Day 180, 2) the patient reaches a dose that is not tolerated, 3) the patient's exposure exceeds that of the no observed adverse effect level (NOAEL) AUC [REDACTED], or 4) the patient's exposure following dose escalation is predicted to exceed that of the NOAEL [REDACTED], whichever comes first. During the

Extension Period, patients who were de-escalated from the final tolerated dose for reasons other than safety or PK considerations may be re-escalated up to their maximally tolerated dose.

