### 4.3 Patient Exclusion Criteria

Current or planned treatment with another investigational drug or device, with the exception rcPMP treatment, through Day -1.

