### 5.2 Prior and Concomitant Medications and Procedures

Prior medications (any drug or substance taken by the patient within 28 days prior to the time the patient's parent or legal guardian signs the informed consent until the first dose of study drug) and concomitant medications (any drug or substance taken by the patient after the first dose of study drug until completion of the last study visit) will be recorded on the patient's CRF/eCRF. Prior procedures (any therapeutic intervention [eg, surgery/biopsy, physical therapy] performed within 28 days prior to the time the patient's parent or legal guardian signs the informed consent until the first dose of study drug) and concomitant procedures (any therapeutic intervention [eg, surgery/biopsy, physical therapy] performed after the first dose of study drug until completion of the last study visit) will be recorded on the patient's CRF/eCRF. If possible, elective surgical procedures should not be performed during the 6-Month Initial Treatment Period.

The use of concomitant medication or concomitant procedure as defined above must be recorded on the patient's CRF/eCRF, according to instructions for CRF/eCRF completion. Changes in a patient's seizure medications, including the reason for the change, will be recorded. Adverse events related to administration of these therapies or procedures must be documented on the appropriate CRF/eCRF.

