#### **9.5 Seizure Diary**

At Screening, the patient's parent or legal guardian will be asked to recall the frequency of seizures over the prior month and the patient's history of seizure medication, including the start and stop dates, dose, and frequency of each seizure medication. The patient's parent or legal guardian will be given a diary to be used to record data regarding the frequency of seizures and any changes in seizure medication for the entire duration of the study.

The Investigator or designee will collect the diary at study visits [REDACTED], record diary data entered by the parent or legal guardian into the CRF/eCRF, and issue a new diary. The diary will be reviewed to identify any medications that were administered for a flurry of seizures or a prolonged seizure and if any changes in seizure medications were made since the last study visit.

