### 13.7.2 Secondary Efficacy Analyses

The secondary efficacy endpoints include:

- Change from baseline in urine and blood SSC levels
- Change from baseline in clinical findings from neurologic examination
- Change from baseline in age-appropriate motor and cognitive assessments (Bayley--III, GMFCS, WPPSI)
- Change from baseline in seizure frequency
- Change from baseline in neuroimaging
- Changes in growth parameters (body weight, body length, head circumference)
- Change from baseline in feeding patterns

Baseline is defined as the last available assessment prior to treatment with ORGN001 except for blood and urine biomarkers whereby baseline is defined as the average of all available assessments prior to treatment with ORGN001.

Observed urine and blood SSC levels as well as changes and percentage changes from baseline to the study time points will be summarized. Individual patient plots over time will be produced.

Shifts from baseline in clinical findings from neurologic examination and neuroimaging findings will be presented for the different time points. The frequency of seizures will be summarized.

Observed values and changes in GMFCS, WPPSI, and Bayley-III cognitive, language, and gross and fine motor scores will be summarized.

Growth parameters (weight [kg], length [cm], and head circumference [cm]) will be converted to age-adjusted z-scores and descriptive statistics will be presented for each parameter over time. In addition, the following individual patient's growth charts will be produced as specified in the statistical analysis plan (SAP) with a flag for start of ORGN001 infusion: Weight-for-age percentiles, length-for-age percentiles and head circumference-for-age-percentiles.

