6.1.3.2. Disease Characteristics

The following disease characteristics will be summarized:

- Age at onset of first MoCD signs/symptoms (days)
- Age at genetic diagnosis (days)
- MoCD Presenting signs and symptoms

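### The SSC baseline averages samples whatever rcPMP dose they were taken on, and eligibility sets no minimum time on rcPMP or stable dose, so a recent rcPMP start or dose change can appear as change on ORGN001

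*Protocol*

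**What the plan says.** The inclusion criteria (Protocol Synopsis and 4.2) are genetic confirmation, consent, and being "Currently treated with rcPMP infusions". The single exclusion criterion (4.3) is "Current or planned treatment with another investigational drug or device, with the exception rcPMP treatment, through Day -1". These lists carry no redaction, and neither requires a minimum time on rcPMP or an unchanged dose. During Screening, children stay on daily infusions of their current rcPMP.

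Protocol 13.7.2 takes the last available pre-treatment value as baseline, "except for blood and urine biomarkers whereby baseline is defined as the average of all available assessments prior to treatment with ORGN001". SAP 8.3 has the same averaging rule, worded by date (on or before the first infusion date) and with the biomarker name blacked out. Table 3 and Section 10 of the Protocol show what normally enters the average: one sample at each of two Screening visits, plus one before the first infusion on Day 1.

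On how rcPMP doses were set, Protocol 1.5 says: "The dosing regimen in patients currently treated with rcPMP has been guided by clinical improvement and urine levels of SSC and thiosulfate". Protocol 1.2 reports that highly elevated urinary SSC was corrected once rcPMP was started.

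Change and percentage change in SSC are summarized (Protocol 13.7.2, SAP 6.2.2.7) under an objective worded as the effect of ORGN001. The study enrolls at least 4 patients and has no control group. No subgroup or sensitivity analysis is planned (SAP 6.2.1.2, 6.2.1.5). The readable disease characteristics in SAP 6.1.3.2 are ages at first symptoms and at genetic diagnosis, and presenting signs. They include no rcPMP history.

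**The concern.** In a single-arm switch study, change from baseline means something only if the level before the switch has settled. Protocol 1.6 rests its efficacy argument on this: no change in clinical status after the switch is to show that ORGN001 is comparable to rcPMP. Nothing in eligibility or in the baseline rule secures a settled level.

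Because rcPMP dosing was steered by SSC, a dose increase prompted by a high value is a plausible event shortly before enrollment. A sample taken before that increase would stay in the average and pull the baseline above the level at which ORGN001 was started. The difference would then count as an ORGN001 effect. With about 4 children, one such child can move the group mean visibly, and no alternative baseline is planned that would show it.

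**Working it through.** The plan gives no figure to reproduce: there is no power calculation, and the number of patients is set by availability. The figures below illustrate the mechanism. SSC ratios, half-lives and sampling days are assumptions; the documents fix only that there are two separate Screening visits within Days -21 to -1 and a pre-infusion sample on Day 1. SSC is expressed relative to its level at the switch.

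**A. Dose change inside the baseline window, no change after the switch.** If m of 3 samples were taken on an earlier dose with SSC r times the switch level, baseline = (m·r + 3 − m)/3 and apparent change = 1/baseline − 1.

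| r | 1 of 3 samples earlier | 2 of 3 samples earlier |
|---|---|---|
| 1.5 | 3.5/3 = 1.167, -14% | 4/3 = 1.333, -25% |
| 2 | 4/3 = 1.333, -25% | 5/3 = 1.667, -40% |
| 0.8 (dose had been lowered) | 2.8/3 = 0.933, +7% | 2.6/3 = 0.867, +15% |
| 0.5 (dose had been lowered) | 2.5/3 = 0.833, +20% | 2/3 = 0.667, +50% |

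A baseline limited to samples on the dose in force at the switch gives 0% in every row.

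**B. SSC still falling at a constant dose up to the switch, then held.** With half-life h and samples t days before the first infusion, baseline = mean of 2^(t/h).

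| h (days) | First sample Day -21 (t = 21, 1, 0) | First sample Day -7 (t = 7, 1, 0) |
|---|---|---|
| 7 | (8 + 1.104 + 1)/3 = 3.37, -70% | (2 + 1.104 + 1)/3 = 1.37, -27% |
| 14 | (2.828 + 1.051 + 1)/3 = 1.63, -39% | (1.414 + 1.051 + 1)/3 = 1.16, -13% |
| 30 | (1.625 + 1.023 + 1)/3 = 1.22, -18% | (1.176 + 1.023 + 1)/3 = 1.07, -6% |

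All three samples here are on the same dose, so a same-dose rule removes none of them and these figures stay as they are.

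**C. SSC falling to a plateau after rcPMP start, the two drugs identical.** SSC = 1 + (R − 1)·2^(−t/h), with t now the days since rcPMP start, R = 5 to 20 and h = 1 to 14 days. Samples are on Days -21, -1 and 1, read out at Day 180.

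| rcPMP start before first sample | Averaged baseline | Day 1 value alone |
|---|---|---|
| 0 days | -57% to -92% | 0% to -87% |
| 21 days | 0% to -79% | 0% to -70% |
| 60 days | 0% to -36% | 0% to -26% |
| 180 days | about 0% | about 0% |

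Example: start 21 days before, R = 5, h = 7. The samples are 1.5, 1.069 and 1.0625 and their mean is 1.21, giving -17%. The Day 1 value alone gives 1/1.0625 − 1 = -6%. Averaging enlarges the spurious fall, but the Day 1 value is also biased if SSC is still falling at the switch.

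**Effect on a mean of 4, the other three children at 0%.** One child at -25% moves it by 25/4, about 6 points. One child at -70% moves it by 70.3/4, about 18 points.

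**The case against.** The strongest reply is that no document shows a recently started or changed child. Recruitment is through physicians already treating patients with rcPMP, children continue their current treatment through Screening, and Protocol 1.5 describes past dosing. For long-treated children the bias is about nil. This stands: a reader might infer that rcPMP effects will be credited to ORGN001, but the documents support only that they can be.

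The phrase covering all available assessments sets no look-back limit, and a reader might infer that old values flood the average. Protocol Section 10 ties baseline to the Screening samples and adds a Day 1 pre-infusion sample, so normally about three values within three weeks are involved.

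A reader might also infer that affected children could not be found in any summary. That is not supported. Current rcPMP falls under prior medications, "any drug or substance taken by the patient within 28 days prior to the time" of consent, which are summarized and listed (SAP 6.1.5). Individual SSC plots are planned, and the output appendices are blacked out. What remains is that the readable baseline summary has no time on rcPMP or last dose change.

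Nor do the documents show that the seizure baseline covers time before rcPMP. Guardians are "asked to recall the frequency of seizures over the prior month", but a diary is dispensed at the first Screening visit and the Protocol baseline for seizures is the last available assessment.

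Finally, averaging repeated values reduces noise and regression to the mean, and the study is descriptive with no primary efficacy endpoint. Both are true. They argue for keeping an average, but not for mixing dose levels within it.

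**Conclusion.** The point holds in conditional form. Under the rules as written, a change of rcPMP dose inside the baseline window produces an SSC change that does not belong to ORGN001, downward after an increase and upward after a decrease. A recent rcPMP start can do the same while SSC is still falling. Children settled on rcPMP are unaffected, and how many are not cannot be told from the documents.

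The size depends on assumed inputs: -14% to -25% for one of three samples at 1.5 to 2 times the switch level, and about -70% to -18% (first sample Day -21) or -27% to -6% (first sample Day -7) for SSC still falling with a half-life of 7 to 30 days. The larger figures need the earliest permitted first sample, so they are an upper illustration and not an expected bias. This is an inexpensive improvement to how SSC change is read, not a flaw that undermines the safety objective.

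**What to change.** Eligibility and dosing stay unchanged.

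1. In Protocol 13.7.2 and SAP 8.3, average only Screening and Day 1 pre-infusion SSC samples taken on the rcPMP dose in force at the switch. The Day 1 sample always qualifies, so a child loses the baseline only if that sample and every other same-dose sample are missing.
2. In SAP 6.1.3.2, add time on rcPMP, rcPMP dose at the switch, and date and direction of the last rcPMP change. First confirm that the date of first rcPMP treatment is captured, because the prior-medication record is defined by use in the 28 days before consent.
3. Step 1 does not correct SSC still falling on a constant dose. Therefore flag children with a recent rcPMP start or change, with the window fixed in the SAP beforehand. Show SSC change with and without them, and also against the Day 1 pre-infusion value alone. A 28-day window would miss slow decline (tables B and C), so time on rcPMP should be listed for every child.

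The cost is SAP wording, a matching protocol edit, a few derived variables and possibly one added data field. The downside is that a flagged child's baseline may rest on fewer samples and so be noisier. With about 4 children the with-and-without display is descriptive only.
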